## **8.3 Study Power and Significance**

P values of <0.05 will be used to determine statistical significance and 2-sided P-values will be reported. Corrections for multiple comparisons will not be employed.

## **8.4 Statistical plan deviations**

Any deviations to the original statistical plan will be reported to relevant ethics and governance committees, and in the manuscript.

## **8.5 Selection of participants for analyses**

Fully detailed in section 4.3. All participants newly diagnosed with T1D in the 12 months following study commencement along with historical controls identified from WACDD, will be included in the primary analysis.

Data for the historical cohort is available on WACDD. Parents of PCH patients and PCH patients aged over 16 years of age are provided with an information sheet and consented to have their health information recorded in the PCH component of the shared database (WACDD, HREC Ref 2013051EP), for clinical, audit and research purposes.

## **8.6 Data Management**

Any information collected in connection with this project will remain confidential. All project-related information will be stored securely. Following consent, the participant will be provided with a unique study number which will be used on data collection instruments in place of identifying information to protect participant confidentiality.

Consent and questionnaire data will be collected using CAHS REDCap which is a secure web platform hosted on the CAHS network. Sociodemographic and clinical data will be extracted from the Western Australian Children's Diabetes Database (WACDD – 2013051EP) . This database is located on a secure Department of Health server at Perth Children's Hospital accessible only by authorised users.

Pump and CGM data will be extracted from the Department of Endocrinology and Diabetes Glooko, Dexcom Clarity and Carelink accounts. Patients attending clinics will be familiar with these systems and there are no study specific requirements above what participants would normally do for clinic visits.

Data will be extracted by staff trained in the use of the above-mentioned databases and for the purposes of this study will be stored in restricted access files on password protected computers accessible by the research team. Data will be retained indefinitely.

Deidentified data will be shared with the study team at Telethon Kids Institute, Monash and Macquarie Universities for data analysis and publication of the project outcomes.

## **8.7 Procedure for accounting for missing, unused, and spurious (*false*) data.**

Multiple imputation by chained equations (MICE) using predictive mean matching will be used to account for missing data in regression models.

## **9 Monitoring / Audit**

### **9.1 Monitoring, Audit and Regulatory Inspections Statement**

The project investigators/institutions will permit project-related monitoring, audits, and regulatory inspections, providing direct access to source data/documents.

### **9.2 Procedures for Monitoring and auditing**

There are no external monitors for this study. The Coordinating Principal Investigator will collate information on participant recruitment, data collection and adverse events at regular intervals. This information will be presented to the wider diabetes research team consisting of medical professionals, scientists, a biostatistician and a community involvement coordinator with experience and training in research to monitor study progress and safety.

As the data for interstitial glucose is downloaded from proprietary software and collated it will be monitored by the research team to ensure data integrity.

## **10 Quality Control And Quality Assurance**

### **10.1 Compliance statement**

The study will be conducted in compliance with the protocol. All staff involved in this study will have Good Clinical Practice (GCP) certification and will be well-versed in the study protocol including the consent process, adverse event management, and data collection. The project will be supervised by the principal investigator(s) to ensure it is conducted in compliance with the protocol, GCP and regulatory requirements. Information on participant recruitment and retention, participant safety and data collection will be collated and reviewed on a regular basis.

### **10.2 Quality control**

All staff will be trained to ensure appropriate data collection in accordance with ICH-GCP guidelines.

Data will be cleaned by trained staff to ensure quality and data checks will be completed. Statistical tools will be used to assess data completeness. Data completeness will be ensured by using mandatory fields in online survey tools.

The data will be presented at a multi-disciplinary team meeting throughout the duration of the study.

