## 7. Questionnaires

### Psychological measures

Participants will be emailed a link for the following surveys to be completed online using REDCap.

- Anxiety: GAD-7 (parent, child >12 years) (18)
- Pittsburgh Sleep Quality Index (parent, child >12 years) (19)
- Diabetes Treatment Acceptance and Satisfaction Questionnaire (DTSQ) (DTSQ-Teen, DTSQ-Parent) (21)\*
- DTSQ Change (DTSQc) (DTSQc-Teen, DTSQc-Parent) (21)
- Hypoglycaemic Fear Survey (Child version) (22)

Type 1 Diabetes and Life Measure (T1DAL) (parent, child >8 years) (23) and Problem Areas in Diabetes (PAID) (Parent and Child Versions) (24) questionnaires are collected as part of routine clinical care at the PCH Diabetes Clinic.

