# 7 Assessment of Safety

## 7.1 Risks and Benefits

This is a low risk, non-invasive study. There are no invasive or painful procedures anticipated.

Foreseeable risks include the potential for psychological distress from responding to the psychological questionnaires, some of which are routinely collected in the clinical setting. In the case where the additional measures collected through REDCap result in any psychological distress, study participants will have access to a Child and Adolescent Health Care Practitioner and study investigators to discuss their distress or aid them in seeking other avenues for mental health support (eg: GP review for mental health care plan where individuals can access free/subsidised sessions with a mental health professional in the community).

It will be explained to the participant that their involvement in the study is entirely voluntary and that they can withdraw from the project at any stage without affecting their relationship with the health professionals or researchers at Perth Children's Hospital. When a participant withdraws a follow-up phone call will be made to ascertain the reason for withdrawal, complete the exit DTSQ and to refer him/her to other services if required.

Benefits to the participant include the following:

- Participants will be able to be involved as consumer advocates for children, adolescents, families and caregivers living with T1D and improved access to diabetes technology.
- Participants may benefit from the reflection that follows answering the types of questions asked in the study.

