## 7.2 Safety

Adverse events are unlikely, however if any participant experiences distress, they will be offered the opportunity to not answer questions, or to discontinue their involvement in the study. At all clinical visits a diabetes social worker is available to support families experience high diabetes distress or experiencing other adverse wellbeing.

Participants will have full access to their usual diabetes clinical triage line and diabetes on-call service outside of office hours if they need to discuss diabetes management, or to be referred for psychological assistance as deemed necessary by the clinical team. After hours psychological assistance in the community is available. This information will be provided in hard copy and included will be the contact details needed to access the services.

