## **8.2 Sample Size**

Over a 12-month period at PCH there are 130-150 children newly diagnosed with T1D depending on annual variation. With a similar sized historical cohort, we expect sufficient power (>80%) to detect moderate effects (greater than 0.35%) in our primary analysis.

With regard to the prospectively collected data, we expect at least 80% uptake of this study, resulting in approximately 105-121 patients to be consented to make up the contemporary cohort.

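### Mandatory survey fields (section 10.2) conflict with the promise that distressed participants may leave questions unanswered (section 7.2), and nothing in the protocol reconciles the two

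*Protocol*

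**What the plan says.** Section 10.2 sets the completeness rule: "Data completeness will be ensured by using mandatory fields in online survey tools". It states no exception.

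Section 7.1 names the risk that matters here: "Foreseeable risks include the potential for psychological distress from responding to the psychological questionnaires". Section 7.2 gives part of the response. For a participant who experiences distress, "they will be offered the opportunity to not answer questions, or to discontinue their involvement in the study".

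Section 4.7.2.3, under Psychological measures, fixes how most of the instruments are delivered: "Participants will be emailed a link for the following surveys to be completed online using REDCap". The list is the GAD-7, the Pittsburgh Sleep Quality Index, the DTSQ, the DTSQ Change and the Hypoglycaemic Fear Survey. T1DAL and PAID are different, since these "questionnaires are collected as part of routine clinical care at the PCH Diabetes Clinic".

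The CHU-9D appears under Health-economic measures with no delivery route of its own. However, section 4.7.2.2 counts general quality of life among the additional questionnaires and sends those not routinely collected in clinic through REDCap. Section 8.6 also places questionnaire data in REDCap.

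Section 4.6(b) excludes a withdrawn participant's research data. Clinical data held in WACDD are kept unless that consent is withdrawn as well. On missing data, section 8.7 says: "Multiple imputation by chained equations (MICE) using predictive mean matching will be used to account for missing data in regression models".

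**The concern.** The option not to answer is one of the protections offered against the one foreseeable risk that the protocol names. A mandatory field, in its ordinary sense, removes that option at the point of use. Questionnaires may be completed away from clinic (section 4.7.2.2), so a staff member able to waive an item need not be present.

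Two things are at stake. The first is that a safeguard described to the ethics committee may not be available on the form. The second is data quality. A person who would skip one item may instead give an untrue answer, leave the form or stop taking part. If those people differ in distress from the rest, the psychosocial summaries at pump start, 12 and 24 months could be affected. So could the CHU-9D utilities that feed the QALYs in section 8.1. The multiple imputation in section 8.7 is stated for regression models, whereas section 8.1 mainly summarises the psychosocial measures descriptively.

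**Working it through.** No sample size, power or alpha figure is in dispute. The check is a comparison of text, followed by an illustration of scale.

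**1. Do the two rules cover the same forms?** Section 10.2 covers online survey tools. Section 7.2 covers questions that may cause distress, which section 7.1 identifies as the psychological questionnaires. Section 4.7.2.3 delivers five of those instruments through REDCap, so the rules overlap on them. The CHU-9D is covered by inference from sections 4.7.2.2 and 8.6. T1DAL and PAID are routine clinic measures and are not stated to use the survey tool.

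**2. Can both rules be followed as worded?** One requires a response in the field; the other allows none. They agree only if the mandatory field contains a response meaning that the person declines. The protocol describes no such response, no bypass and no waiver procedure.

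**3. What options remain for someone who does not want to answer?** Answer untruthfully, leave the form, or discontinue. The last engages section 4.6(b). The study-specific questionnaires from every wave are excluded, while WACDD data remain.

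**4. Number exposed.** Section 8.2 says: "we expect at least 80% uptake of this study, resulting in approximately 105-121 patients to be consented". From 130-150 diagnoses a year, 0.80 × 130 = 104 and 0.80 × 150 = 120, which matches the stated 105-121 to within one patient. This applies to instruments answered for every participant (parent GAD-7, CHU-9D). Fewer answer the child GAD-7 and sleep index, which are limited to children over 12 years.

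**5. Illustration of scale.** Let q be the chance that a respondent refuses a given item and k the number of items. If refusals are independent, the share of forms with at least one refusal is 1 − (1 − q)^k. The protocol gives neither q nor k. I assume q from 0.5% to 5%, and k = 7 and k = 9, read from the names GAD-7 and CHU-9D.

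| q | k = 7: share | of 105-121 | k = 9: share | of 105-121 |
|---|---|---|---|---|
| 0.5% | 3.4% | 3.6-4.2 | 4.4% | 4.6-5.3 |
| 1% | 6.8% | 7.1-8.2 | 8.6% | 9.1-10.5 |
| 2% | 13.2% | 13.8-16.0 | 16.6% | 17.5-20.1 |
| 5% | 30.2% | 31.7-36.5 | 37.0% | 38.8-44.7 |

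For example, with q = 1% and k = 7: 1 − 0.99^7 = 0.068, and 0.068 × 105 ≈ 7.1.

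These are forms with a refused item. They become lost forms only if every such form is abandoned or discarded, which the protocol does not say. Refusals also tend to cluster in the same people, which lowers the share for a given q. The range runs from negligible to material, and the protocol does not settle where the trial would fall.

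**The case against.** The strongest reply is that the conflict is one of wording. Section 10.2 does not say that every item is mandatory or that submission is blocked, and REDCap also holds consent, so the mandatory fields might be others. A decline response inside a mandatory field would satisfy both sections. Section 7.2 is a conditional offer to a distressed participant and could be met by leaving a whole questionnaire undone. Other supports exist: a health practitioner and the investigators, a social worker at clinical visits, the triage line, and voluntary withdrawal. Participants are also selected for willingness to complete questionnaires (sections 4.4 and 4.5).

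Part of this stands. The protocol does not establish that forms will be blocked, and the safeguard does not rest on item skipping alone. But section 7.2 speaks of not answering questions, which most naturally means items. Section 10.2 relies on mandatory fields to secure completeness, which works for a questionnaire only if its items are among them. That a decline response could reconcile the two does not mean that the protocol provides one.

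A reader might go further and infer that single skipped items will become lost questionnaires, and that scores will look better than they are because the most distressed leave. The documents do not support either step. No section says that partly completed forms are rejected or discarded, and nothing indicates who would refuse or in which direction scores would move.

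**Conclusion.** The point holds as an unreconciled conflict between two stated rules. Sections 7.2 and 10.2 cannot both be followed as worded on the REDCap questionnaires. Form construction and participant safeguards are matters that this protocol itself fixes, so the conflict cannot be left to an SAP.

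The effect on the data is possible but of unknown size. A reader might take a refusal rate of 3-10% and infer a loss of about 3 to 12 participants per form (0.03 × 105 = 3.15; 0.10 × 121 = 12.1). That rate is an assumption with no basis in the protocol, so the result should not be quoted as an expected loss. The same applies to the table above.

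The scope is limited. The HbA1c primary analysis uses routine WACDD data and is untouched, and T1DAL and PAID lie outside the conflict. The exposed data are the REDCap psychosocial measures and, if delivered the same way, the CHU-9D. The CHU-9D deserves most care because its comparator utilities come from an external survey (section 8.1). Any selective loss on these forms would therefore fall on the contemporary cohort only.

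**What to change.** Replace the sentence on mandatory fields in section 10.2 with: *Questionnaire items in REDCap will be mandatory and will each include a 'prefer not to answer' response, recorded separately from other missing data.*

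This keeps the completeness control, since nothing can be passed over by accident. It makes the section 7.2 offer available on the form and lets refusals be counted apart from other missing values. There is no need to remove mandatory fields or to forbid any item from blocking submission. Scoring rules for partly completed instruments can stay with the SAP or the data-management plan.

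The cost is one sentence and a change to the form set-up. The downside is a few more item-level missing values, because some people who would have answered when required will choose to decline.

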## **11 Ethics**

Participants are informed that their consent is voluntary and their participation in the study or not will not affect their treatment in the clinic. Consent will be obtained from the participants and their guardian prior to study commencement, and they will be informed that they are able to withdraw at any point.

## 12 Budget, Financing, Indemnity And Insurance

This is an investigator led project. All investigators and study personnel are indemnified by their employing institutions.

This project is funded by a WA Child Research Fund grant supported by the Government of Western Australia and Channel 7 Telethon Trust.

## 13 Publication

The results of this study will be disseminated in a peer reviewed manuscript, presented at local and international conferences, shared with all participants and the general T1D community via email, the Children's Diabetes Centre patient newsletter and the T1D Collaborator (aimed at stakeholders, researchers and collaborators nationally and internationally) and social media, and Diabetes Community organisations.

